Title: Evaluation of the Necessity of Operative Irrigation and Debridement: Pediatric Randomized trial of type One Open Fractures (PROOF)

Author: [name]

Version Date: 06/01/2015

A. Scientific Aims:

Clinical Trial Portion:

1. Do patients with type one open fractures treated in the emergency department with irrigation have a non-inferior rate of infections compared to those treated in the operating room with formal irrigation and debridement? The response variable will be the presence of an infection in children with open fractures.
2. Do patients with type I open fractures who are treated nonoperatively have a non-inferior time to bone healing when compared to those treated operatively? The response variable will be time to clinical and radiographic fracture healing.

Hypothesis: Minor open fractures in children can be safely treated in the emergency room with irrigation, closed reduction and home antibiotics without an increased risk of infection or a longer time to healing.

- a. Null Hypothesis: Open fractures treated in the emergency room will have a higher rate of infection, and a longer time to complete healing.

Survey Portion:

3. What are the current attitudes among members of the Pediatric Orthopaedic Society of North America (POSNA) toward the treatment of type one open fractures in the pediatric population?

Hypothesis: There will be no consensus in the treatment of type 1 open fractures in the pediatric population in regards to whether or not formal irrigation and debridement is necessary, antibiotic use, and timing for fractures.

A. Significance:

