Patients will be recruited from the emergency department at the participating hospitals. All patients with open fractures (fractures associated with a skin wound) who present to emergency department will be assessed for inclusion. The initial assessment of open fracture will be identified by the emergency room physician who will discuss with the attending on call. The orthopaedic attending will determine if this child is amenable to non-operative treatment and would be considered for study inclusion.

All children will be given antibiotics (Ancef 25mg/kg up to 1gm, or clindamycin if allergic to first generation cephalosporin or penicillin) and if the inclusion criteria are met, will be offered to participate in the study by the orthopaedic surgeon or their delegate. If the patient refused study inclusion, they will then be treated per the attending treating physician recommendation.

If the patient agrees to participate he/she will be randomized. The randomization chart is saved in the REDCap database and functions to randomly assign a patient who is entered into the database into a treatment group, stratifying by site. The attending physician will be responsible for determining the randomization assignment by either (1) logging into the REDCap database to enter the patient and randomize them or (2) calling the research coordinator or his/her representative who will then log in to REDCap to randomize the patient. As a backup, the research coordinator will have the randomizations for each site in numbered, sealed envelopes. The study coordinator will be available 24 hours a day to provide the randomization assignment, the consent form (see consent process below), and answer questions prior to treatment arm assignment. Children in both arms of the study will receive emergency room irrigation with one liter of normal saline, realignment/reduction of the fracture, and casting. Conscious sedation will

usually be necessary for this to occur. Patients will be admitted and have up to 24 hours from the time of injury to make a final decision.

No difference in outcomes have been shown in patients with open fractures treated with operative debridement in less than 6 hours compared with those treated from 6 to 24 hours.(8) The surgical timing will be determined by the attending orthopaedic surgeon.

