Baseline assessment will include the child's age, mechanism of injury, bone fractured, wound side and location, state of skin injury, whether gross contamination is present, neurovascular status, comorbid conditions.

Additionally, if patients do not wish to be randomized to a treatment arm, they will still be presented with an option for study enrollment. They may take part in a prospective chart review in which the same data will be collected as those patients who were randomized. The data collected at both the baseline and follow-up will match the data collected from patients who randomized to a treatment arm. Patients will consult with their physician regarding treatment for their injury and decide which treatment method they prefer. They will then be consented by the study coordinator or an investigator who will describe the study and the data that will be gathered from their medical charts.

Intervention allocation:

The randomization assignment will be completed and accessible only by the study coordinator. The coordinator will have the assignments in numbered, sealed, radio opaque envelopes in sequential order by the study site. The envelopes will be made by an independent study assistant and determined by block allocation with a 1:1 ratio of operative room vs. emergency room management with permuted, mixed blocks of 4 and 6 created randomly. Randomization will be stratified by each center but by no other factors. The order of these permuted blocks will be determined by random number chart.

Experimental and Control Interventions:

Children will be randomized into two treatment arms – formal operative management (OR) and emergency department (ED) management. Children randomized to the OR arm will be taken to the OR within 24 hours for irrigation and debridement and appropriate bone management. Patients who randomize to non-operative treatment will only be given conscious sedation in the emergency department where the bone will be reduced and casted and the wound will be washed out with one liter of normal saline. All patients will be admitted for 24 hours of intravenous antibiotics post treatment and then sent home with 7 days of oral antibiotics.

Follow up visit description and schedule:

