(Specific Aim 2) Union of the fracture will be determined by radiographic parameters of callous being on three of four sides of bone without tenderness to palpation. The radiographs will be read by the attending orthopaedic surgeon at each clinic visit to determine treatment. Loss of reduction will be noted but will not be considered a complication since it can occur whether or not operative debridement was performed. A revision reduction can be performed at the attending orthopaedic surgeon's discretion. In the final analysis phase, an orthopaedic surgeon, blinded to the treatment, at Lurie Children's will be utilized to review all of the patient's radiographs to determine bridging callous on three sides of the bone. This reviewer will be blinded to the patient's name, treatment group but will have access to the length of time since the fracture occurred. Additional procedures or deviations from the protocol will be noted. We will

also carefully examine the rates of anesthesia and sedation related complications including nausea and vomiting, respiratory depression, aspiration, hoarseness, and emergence agitation.

Sample size assumptions and estimates:

This will be a non-inferiority trial as we attempt to demonstrate that ED management is not inferior to OR management.

For the binary outcome of infection (**Specific Aim 1**), we estimate an infection rate of 1% in the reference (OR) group since the literature notes an infection rate between 0% and 5%. Based on a survey of pediatric orthopedic surgeons, an acceptable margin of non-inferiority can be estimated at approximately 4% (i.e., accept a 5% infection rate in the ED group), as the survey suggests surgeons will accept a 5% infection rate in order to avoid formal operative treatment of children with open fractures. We will test the following hypotheses: $H_0: P_T - P_C \geq \Delta$ vs. $H_1: P_T - P_C < \Delta$. In order to test these hypotheses in a non-inferiority design at the one-sided 2.5% level of significance, we will construct a two-sided 95% confidence interval for the difference in proportion of infections ($P_T - P_C$) across the two groups. If the upper confidence limit is less than our acceptable margin of non-inferiority ($\Delta=4\%$), then we would conclude ED management is not inferior to OR management with respect to infection rates.

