The main ethical issue associated with this research would be if there is an increased infection rate with children who are randomized to the non-operative arm. These children may require longer term antibiotics or additional surgery. However, if a single surgery is ultimately necessary, the patient may only have lost minor healing time since a surgery was saved initially. Due to the fact that there are now three case series reporting children treated nonoperatively for minor open fracture, multiple centers are using it as their standard treatment practice. While these retrospective studies do not demonstrate an increased infection rate, these case series were all underpowered to show a significant difference. In our survey to POSNA membership, 31% of respondents chose emergency room treatment while 69% chose an operative strategy in the treatment of type I open forearm fracture. Therefore, equipoise exists for this question. The main benefit of this study will be to future children with open fractures. The children in the study will benefit if they were randomized to the ED group and the data shows no signs of infection and a normal healing time because they will have avoided a trip to the operating room.

Risks to Participants:

Patients with Type I open fractures are generally at minimal risk of problems if treated appropriately. The fracture should be treated within 24 hours of the injury to avoid infection. Infections may be caused by bacteria that contaminate the wound at the time of injury. Infections are unusual with this injury and can occur whether the child is taken to surgery. Infection may result in slow healing of the fracture and chronic bone infection. All children with fractures may also experience injury to the nerves or arteries or excessive swelling which can cause injury to muscle tissue. Risks of anesthesia in the Emergency Department or operating room may include breathing problems but are very rare in a previously healthy person. Participants who undergo surgery will be told of the risks related to anesthesia and surgery at that time and will sign a separate, treatment consent for the surgery and anesthesia. Risks of fracture treatment may include alignment problems or poor bone healing. Unknown risks may be involved with this research study.

Benefits:

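### Loss of reduction is ruled out as a complication for a reason that does not hold in a randomised comparison, and no planned analysis compares it by arm

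*Combined protocol and SAP*

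**What the plan says.** Under Ascertainment of response variables (Specific Aim 2), the plan says: "Loss of reduction will be noted but will not be considered a complication since it can occur whether or not operative debridement was performed". The next sentence adds: "A revision reduction can be performed at the attending orthopaedic surgeon's discretion". The trial is unblinded.

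Five other places bear on this:

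- **Risks to Participants**, on infection: "Infections are unusual with this injury and can occur whether the child is taken to surgery".
- **Study Procedures**: "Children in both arms of the study will receive emergency room irrigation with one liter of normal saline, realignment/reduction of the fracture, and casting".
- **Experimental and Control Interventions**: children in the OR arm are then "taken to the OR within 24 hours for irrigation and debridement and appropriate bone management", while those in the ED arm "will only be given conscious sedation in the emergency department where the bone will be reduced and casted".
- **Scientific Aims**: the hypothesis is that these fractures "can be safely treated in the emergency room with irrigation, closed reduction and home antibiotics without an increased risk of infection or a longer time" (the time meant is that until the fracture heals).
- **Data management**: the state of the reduction is recorded at the 1-week visit and at later visits.

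The Data Analysis section that follows Data management, and Final analysis, cover infection, healing time, additional procedures and anesthesia complications. Neither lists loss of reduction. The adverse-event grades under Interim monitoring are written around infection and debridement.

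**The concern.** The plan gives one reason for not counting loss of reduction: it can happen with or without debridement. That describes almost any outcome worth randomising for. If an event can occur in both arms, the trial can estimate whether it occurs more often in one of them. An event possible in only one arm would need no comparison.

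Closed reduction in the ED is part of the strategy under test. Whether the reduction holds is a natural question about that strategy, and the trial already collects the data to address it. Under the current text, readers would get no prespecified between-arm estimate. They could not tell whether the absence of a reported difference means that there was none or that nobody looked.

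**Working it through.** **Is the stated reason applied consistently?** The plan says of both loss of reduction and infection that they can occur whether or not the child has surgery. Infection is the Aim 1 outcome; loss of reduction is not counted. Anesthesia and sedation complications can also arise in both arms, and the same section says their rates will be examined. Occurrence in both arms is therefore not the plan's criterion elsewhere, and no other reason is offered.

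**Could the arms differ?** Both start with ED reduction and casting. The OR arm then has a further opportunity to manage the bone; the ED arm has reduction under conscious sedation only. Against this, Study population requires fractures amenable to closed reduction and excludes those that would typically need operative reduction and fixation. A difference is possible but not shown.

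**Does any planned analysis pick it up?** The nearest is the confidence interval for the number of additional procedures in Final analysis. Revision reductions could be counted there. But the count does not separate fracture from wound procedures, it omits displacement that is left alone, and revision is at the discretion of an unblinded surgeon. It is an imperfect proxy.

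**How precise would a comparison be?** The plan gives no rate for loss of reduction, so there is no figure of its own to reproduce on this point. The input taken from it is 150 per arm. (The plan's 91% power for infection at that size does reproduce: exact enumeration of the Wald interval gives 0.9105 against 0.9111 in its table. Nothing here alters it.) All rates below are assumptions.

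With equal rates p in both arms, the 95% half-width for ED minus OR is 1.96 × √(2p(1−p)/150):

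- p = 5%: 1.96 × √(0.095/150) = 4.9 points
- p = 10%: 1.96 × √(0.18/150) = 6.8 points
- p = 20%: 1.96 × √(0.32/150) = 9.1 points
- p = 30%: 1.96 × √(0.42/150) = 10.4 points

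For 10% OR versus 20% ED (15 versus 30 children):

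- Standard error = √(0.20 × 0.80/150 + 0.10 × 0.90/150) = 0.0408.
- If exactly that difference were observed, the interval would be 0.10 ± 1.96 × 0.0408 = 0.10 ± 0.080, or about 2 to 18 points.
- Power at two-sided 0.05 is Φ(0.10/0.0408 − 1.96) = Φ(0.49), about 69% (68% with a pooled null variance).

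For 80% power, OR rates of 5%, 10%, 20% and 30% would need ED rates of about 14.6%, 21.8%, 34.4% and 45.7%.

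**The case against.** The case for leaving the text alone has several parts.

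- **Scope of the safety claim.** A reader might infer that a harm is being hidden from a general claim of safety. The hypothesis does not support that: its full sentence ties safe treatment to infection and healing time.
- **No pooled complications endpoint.** A reader might also infer that the ED arm could lose reduction much more often and the trial would still report no excess of complications. The plan contains no such overall result, so the label by itself changes no listed analysis. This objection stands, but what is missing is still the comparison.
- **Attribution.** The sentence can be read as saying that loss of reduction is not specific to debridement, whereas infection is what debridement is meant to prevent. That is fair as to intent. But the trial compares two whole strategies, and they differ in bone handling as well as wound handling.
- **Aim 2 may absorb it.** If re-reduction delayed union, the delay would enter healing time. That is so, but the documents do not say that re-reduction delays union, and displacement that heals on time would not show there.
- **Measurement.** The protocol does not define loss of reduction. Unblinded attending surgeons record it, and the blinded reader's stated task is bridging callus only. This stands and limits what a comparison can bear.

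**Conclusion.** The point holds as an improvement to a stated rule. The reason given for excluding loss of reduction is invalid and is not applied to infection, and no planned analysis compares this harm by arm, although reduction status is already recorded.

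Two stronger conclusions are not supported. The documents do not show that ED treatment loses reduction more often: both arms have ED reduction, fractures typically needing operative fixation are excluded, and no rates are given. Nor would an excess be easy to detect: a doubling from an assumed 10% has about 69% power. With 150 per arm and assumed common rates of 5% to 30%, the difference would be known to within about 5 to 10 points either way, which is informative for a secondary safety outcome but imprecise. No primary endpoint, margin, sample size or power figure is affected.

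**What to change.** In Ascertainment of response variables, delete the clause that excludes loss of reduction from complications, together with its reason. Prespecify loss of reduction, and repeat reduction or fixation, as secondary safety outcomes, and state how loss of reduction is determined from the visit data. Report each by randomised arm with the ED minus OR difference and a 95% confidence interval, and keep fracture procedures separate from those done for the wound. If the investigators prefer not to do this, the conclusion should be stated as limited to infection and healing time.

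The cost is about one table, since the visit forms already record the reduction, plus a written definition and a split of procedures by reason. The downsides are that the assessment is made by unblinded surgeons, the estimate will be imprecise, and the result may be unfavourable to the ED arm. Nothing here changes when a revision is performed.

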The following are power estimates based on 10000 simulations under the above conditions for various feasible sample sizes. We also obtained power estimates for the scenario involving a 2% infection rate in the control group (OD).

Sample size/arm	Reference Proportion	Power ($\Delta=0.03$)	Power ($\Delta=0.04$)	Power ($\Delta=0.05$)	Power ($\Delta=0.06$)
70	0.01	0.5091	0.6766	0.8536	0.866
80	0.01	0.5164	0.8107	0.8382	0.9434
90	0.01	0.4865	0.786	0.8734	0.9489
100	0.01	0.7416	0.7878	0.9254	0.9616
110	0.01	0.6994	0.8383	0.9245	0.976
120	0.01	0.6926	0.894	0.9437	0.9763
130	0.01	0.714	0.8738	0.9621	0.981
140	0.01	0.6907	0.8783	0.9624	0.99
150	0.01	0.7606	0.9111	0.9748	0.9928
160	0.01	0.8221	0.9394	0.9816	0.997
170	0.01	0.795	0.9427	0.9842	0.998
180	0.01	0.821	0.9339	0.9876	0.9984
190	0.01	0.8147	0.9573	0.9936	0.9987
200	0.01	0.848	0.9629	0.9928	0.9987
210	0.01	0.8503	0.9669	0.9941	0.9995
220	0.01	0.8675	0.9743	0.9961	0.9992
130	0.02	0.4748	0.6378	0.8123	0.9066
140	0.02	0.4906	0.6922	0.8385	0.9288
150	0.02	0.5051	0.7048	0.8785	0.9466
160	0.02	0.5642	0.7452	0.8678	0.9593

170	0.02	0.5458	0.7621	0.8958	0.9679
180	0.02	0.5651	0.7737	0.9165	0.9682
190	0.02	0.5864	0.8088	0.9317	0.9733
200	0.02	0.5865	0.8005	0.9275	0.9807
210	0.02	0.6349	0.8346	0.943	0.9833
220	0.02	0.61	0.842	0.9504	0.9868

For outcome of healing time (**Specific Aim 2**), most fractures have a healing time of 6 weeks with an estimated standard deviation of 1 week. We will again try to show ED management is not inferior with respect to healing time when compared to OR management, assuming a margin of non-inferiority of one week ($\Delta=1$). Assuming a one-sided 0.025 level of significance and power ($1-\beta$) equal to 0.90, the number of subjects required per treatment group can be calculated as follows:

$$H_0: \mu_C - \mu_T \geq \Delta \quad \text{vs.} \quad H_1: \mu_C - \mu_T < \Delta$$

$$N = \frac{2(Z_{\alpha} + Z_{1-\beta})^2 \sigma^2}{\Delta^2}$$

$$N = \frac{2(1.96 + 1.282)^2 1^2}{1^2} \qquad N = 21$$

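### The stated Aim 2 healing endpoint cannot be built from the blinded reading and the listed visit items, and the blinded reader is told the time since fracture

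*Combined protocol and SAP*

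**What the plan says.** - **Endpoint.** Under Scientific Aims, for Aim 2: "The response variable will be time to clinical and radiographic fracture healing". Under Ascertainment of response variables (Specific Aim 2), union requires "callous being on three of four sides of bone without tenderness to palpation". Both describe a composite of a film finding and an examination finding.
- **Attending's reading.** The same section says: "The radiographs will be read by the attending orthopaedic surgeon at each clinic visit to determine treatment". The Methods describe the trial as unblinded.
- **Central reading.** At the final analysis stage, a surgeon masked to name and treatment group reviews all films "to determine bridging callous on three sides of the bone". This reader "will have access to the length of time since the fracture occurred". Tenderness is not part of the task.
- **Recorded items.** Data management lists, for visits after the first week, fevers, increased pain, wound drainage, a second look at the wound, reduction and healing. Tenderness is not listed.
- **Analysis.** The Data Analysis section that follows Data management, and the Final analysis section, compare healing time by a confidence interval for the difference in means and by Kaplan-Meier curves. Neither names the reading or the union rule that supplies the time.
- **Planning values.** Under Sample size assumptions and estimates: "most fractures have a healing time of 6 weeks with an estimated standard deviation of 1 week", "assuming a margin of non-inferiority of one week", and "Assuming a one-sided 0.025 level of significance and power" of 0.90.

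**The concern.** The plan arranges a masked reading, which is the right protection in an open-label trial, but that reading measures something other than the stated endpoint. It drops the clinical component and asks for bridging callus where the union definition asks for callus. The only listed place where the clinical component could enter is the healing entry of a surgeon who knows the allocation. Two healing times will therefore exist, one masked but incomplete and one possibly complete but unmasked. With no rule choosing between them, the choice could be made after the data are seen.

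The second issue is what the reader knows. The outcome is a time, and each film is judged with its elapsed time visible. A reader who expects union at about 6 weeks may be readier to call a borderline film united near that point. Masking to treatment arm does not prevent this. In a superiority trial, an equal pull in both arms would be conservative. In a non-inferiority comparison it would favour the conclusion being sought.

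**Working it through.** **1. The plan's own figure.** The inputs are SD 1 week, margin 1 week, one-sided 0.025 and power 0.90.

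N = 2 × (1.96 + 1.282)² × 1² / 1² = 2 × 10.51 = 21.02 per group.

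The stated 21 is reproduced (22 if rounded up). The planned 150 per group is far above this, so the issue is measurement and not power.

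**2. Can the endpoint be assembled?**

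| Source | Callus on three sides | No tenderness | Masked to arm |
|---|---|---|---|
| Stated union definition | required | required | not stated |
| Central reader | yes, as bridging callus | not assessed | yes |
| Attending's healing entry | yes | only if implied | no |
| Other listed visit items | no | not listed (increased pain is a different item) | no |

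No combination of the masked reading with a listed item gives callus plus no tenderness. The clinical part can come only from the attending's healing entry.

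**3. Direction of the mismatch.** The documents give no component times, so the following values are assumptions. Time to callus has mean 6 weeks and time to loss of tenderness has mean 5 weeks, both normal with SD 1 and independent. Bridging follows callus by a constant lag, which cancels between arms. The stated endpoint is the later of the two component times, and the central reading depends on callus alone. For two such times with means a and b,

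E[max] = aΦ(k) + bΦ(−k) + √2 φ(k), where k = (a − b)/√2.

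- Reference arm (6, 5): 6.20 weeks.
- Callus delayed by 1 week (7, 5): 7.05. Stated endpoint differs by 0.85; central reading by 1.00. The central reading shows the larger difference.
- Tenderness delayed by 1 week (6, 6): 6.56. Stated endpoint differs by 0.36; central reading by 0.00. The central reading shows the smaller difference.
- Both delayed by 1 week (7, 6): 7.20. Both differ by 1.00. No change.

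The mismatch therefore has no fixed direction. The figures only illustrate this and are not estimates for the trial.

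**4. Direction of anchoring, if it occurs.** Suppose the read time is (1 − w) × true time + w × 6 weeks, with the same w in both arms. The 6w term cancels, so a true ED minus OR delay d appears as (1 − w)d. For any w between 0 and 1 and any positive d, the difference moves towards zero.

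**5. Why no size follows.** The documents say nothing about w. The scale on which it would act is also unsettled. Films are taken at about 1, 2, 4, 6, 12 and 24 weeks, so, if union is dated to the first visit at or after healing, recorded times jump between those values. With SD 1:

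- OR mean 6 weeks, ED mean 7: recorded means are 8.95 and 11.05, so a true 1-week delay appears as about 2.09 weeks (8.954 and 11.046 before rounding).
- OR mean 7 weeks, ED mean 8: the same true delay appears as about 0.82 week.

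A shrinkage worked out on a continuous scale therefore cannot be compared directly with the 1-week margin.

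**The case against.** The strongest defence is that the reader is masked to treatment group, which is what matters most in an open trial, and makes a yes/no judgement on each film. Time is attached to that judgement and is not estimated by the reader. Serial context may also help in reading callus. All of this stands. It makes anchoring a risk and not a demonstrated fault, and it means that masking the dates has a real, if small, cost.

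It can also be said that the attending's healing entry may carry the tenderness finding, since the union definition includes it, and that the visit form itself is not in the documents. That is fair. A separate tenderness field may exist, but the listed items do not show one, and a general healing entry remains an unmasked judgement.

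Three stronger readings are tempting, and the documents do not support them:

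- **That both features pull the arms together.** The definition mismatch can act in either direction or not at all.
- **That anchoring yields a particular inflation of false non-inferiority.** Any such figure rests on an invented weight and on a continuous time scale that the visit schedule does not provide.
- **That the central reading is the analysed endpoint.** The plan never says so. If the attending's assessment is used, the reader's knowledge of time is irrelevant to the result, but the analysis then loses its masking.

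**Conclusion.** The point holds as a low-cost improvement to Aim 2. The plan states a composite endpoint, arranges a masked reading of only one component, lists no separate item for the other, and does not say which reading is analysed. This is more than missing detail, because the two available healing times are not equivalent: one lacks the clinical component and the other lacks masking. The effect on the ED minus OR difference has no predictable sign.

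Telling the reader the elapsed time adds an avoidable risk. If it leads to equal anchoring in both arms, it could favour non-inferiority. That is conditional on three things: that anchoring happens, that it is similar across arms, and that the central reading is the one analysed. Its size is unknown, and none should be quoted.

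The reach is limited to healing time. The 21 per group reproduces, and the total of 300 is set by the infection endpoint, which this point does not touch.

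**What to change.** 1. Add a tenderness yes/no item to every follow-up form.
2. Define the analysed healing time once: the first visit at which the masked reading shows callus on three sides and the form records no tenderness. Settle on one wording for the callus criterion (callus or bridging callus) and use it throughout.
3. Remove dates and time since fracture from the films given to the central reader, present them in random order, and link the dates back afterwards.
4. State that this healing time feeds both the confidence interval and the Kaplan-Meier curves, and report the attending's reading as secondary.

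The cost is one tick box per visit, the work of de-dating and shuffling films, and some loss of serial context for the reader. The central reading takes place at the final analysis stage, so items 2 to 4 need no change to patient contact. The sample size is unchanged.
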